**Table 17: LIST OF PROHIBITED CYP3A INHIBITORS AND INDUCERS**

Strong inhibitors	CYP3A	Moderate inhibitors	CYP3A	Strong inducers	CYP3A	Moderate inducers	CYP3A
clarithromycin		aprepitant		avasimibe		bosentan	
conivaptan		atazanavir		carbamazepine		efavirenz	
grapefruit juice		cimetidine		Phenobarbital (barbiturates)		etravirine	
indinavir		ciprofloxacin		phenytoin		modafenil	
itraconazole		darunavir		rifabutin		nafcillin	
ketoconazole		diltiazem		rifampin		ritonavir	
lopinavir		erythromycin		St. John's Wort		talviraline	
mibefradil		fluconazole				tipranavir	
nefazodone		tofisopam					

Strong inhibitors	CYP3A	Moderate inhibitors	CYP3A	Strong inducers	CYP3A	Moderate inducers	CYP3A
nelfinavir		verapamil					
posaconazole		amprenavir					
ritonavir		fosamprenavir					
saquinavir		elvitegravir					
telithromycin		tipranavir					
troleandomycin							
voriconazole							

This database of CYP inhibitors was compiled from the Indiana University School of Medicine’s “Clinically Relevant” Table and from the University of Washington’s Drug Interaction Database based on *in vitro* studies. Strong inhibitors are predicted to increase BKM120 AUC > 5-fold, and moderate inhibitors are predicted to increase BKM120 AUC  $\geq$  2-fold but < 5-fold.

This database of CYP inducers was compiled from the FDA’s “Guidance for Industry, Drug Interaction Studies;” from the Indiana University School of Medicine’s “Clinically Relevant” Table; and from (Pursche et al. 2008).

**Table 18: LIST OF PROHIBITED QT PROLONGING DRUGS**

All QT-prolonging drugs listed in this table are prohibited for all patients from screening through permanent discontinuation of study treatment. Table 18 lists drugs with a known risk for Torsades de Pointes (TdP) as well as sensitive CYP3A substrates (with narrow TI) with a possible or conditional risk for TdP.

Drug	QT risk(*)	Comment
Amiodarone	Known risk for TdP	Females>Males,TdP risk regarded as low
Arsenic trioxide	Known risk for TdP	
Astemizole	Known risk for TdP	No Longer available in U.S.
Bepidil	Known risk for TdP	Females>Males
Chloroquine	Known risk for TdP	
Chlorpromazine	Known risk for TdP	
Cisapride	Known risk for TdP	Restricted availability; Females>Males.
Disopyramide	Known risk for TdP	Females>Males
Dofetilide	Known risk for TdP	
Domperidone	Known risk for TdP	Not available in the U.S.
Droperidol	Known risk for TdP	
Halofantrine	Known risk for TdP	Females>Males

Drug	QT risk(*)	Comment
Haloperidol	Known risk for TdP	When given intravenously or at higher-than-recommended doses, risk of sudden death, QT prolongation and torsades increases.
Ibutilide	Known risk for TdP	Females>Males
Levomethadyl	Known risk for TdP	
Mesoridazine	Known risk for TdP	
Methadone	Known risk for TdP	Females>Males
Pentamidine	Known risk for TdP	Females>Males
Pimozide	Known risk for TdP	Females>Males
Probucol	Known risk for TdP	No longer available in U.S.
Procainamide	Known risk for TdP	
Quetiapine	Possible risk for TdP	Prohibited as this drug is a sensitive 3A4 substrate
Quinidine	Known risk for TdP	Females>Males
Sotalol	Known risk for TdP	Females>Males
Sparfloxacin	Known risk for TdP	
Tacrolimus	Possible risk for TdP	Prohibited as this drug is a sensitive 3A4 substrate with narrow TI
Terfenadine	Known risk for TdP	No longer available in U.S.
Thioridazine	Known risk for TdP	
Vardenafil	Possible risk for TdP	Prohibited as this drug is a sensitive 3A4 substrate
(*) Classification according to the Qtdrugs.org Advisory Board of the Arizona CERT Sensitive substrates: Drugs whose plasma AUC values have been shown to increase 5-fold or higher when co-administered with a potent inhibitor of the respective enzyme.		

### Drugs to be used with caution

Preliminary in vitro metabolism studies suggest that BKM120 is a weak, reversible inhibitor CYP3A4/5 ( $K_i=13.6 \mu\text{M}$ ,  $[I]/K_i=0.4$  where  $[I]$  is the average  $C_{\text{max}}$  at steady-state following 100 mg daily dose) and a weak reversible inhibitor of CYP2C8/2C9/2C19 ( $IC_{50}=34 \mu\text{M}$ ,  $[I]/IC_{50}=0.15$ ). Note: that with the data available, we are not able to confirm whether such interactions will occur in patients. Therefore, investigators, at their discretion, may administer concomitant medications known to be metabolized by CYP3A4/5, CYP2C8, CYP2C9 and CYP2C19. Patients receiving such medications must be carefully monitored for potentiation of toxicity due to any individual concomitant medications, and may require dose titration or reduction of the drug substrate. Please refer to Table 19 for a list of CYP450 substrates and carefully consider their co-administration with BKM120.

Particularly, caution is advised when BKM120 is co-administered with:

- Drugs which are substrates for CYP3A4, CYP2C8, CYP2C9 or CYP2C19 and which have a narrow therapeutic index.
- Oral anti-diabetics which are metabolized by CYP2C8 or CYP2C9 can possibly result in hypoglycemia. Patients who develop diabetes mellitus during the study should be treated according to the American Diabetes Association guidance. It is recommended that treatment start with metformin.
- If a patient, after study enrollment, requires the concomitant use of any QT prolonging medication with a possible or conditional risk for torsade de pointes then the investigators, at their discretion, may co-administer such medications. Patients receiving such medications must be monitored. Refer to Table 18 for a list of QT prolonging medications to be used with caution.

Note: please refer also to Table 18 for a list of **prohibited** QT prolonging medication.

- Please refer to Table 19 for a list of CYP450 substrates and carefully consider their co-administration with BKM120.
- Concomitant treatment with corticosteroids and BKM120 should be avoided, whenever possible, during this study. A short duration (< 2 weeks) of systemic corticosteroids is allowed (e.g. for chronic obstructive pulmonary disease, or as an anti-emetic). Chronic dosing of corticosteroids is known to induce CYP3A enzymes, thereby increasing the risk or reducing BKM120 overall exposure to sub-therapeutic levels.

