  - Myocardial infarction within the last 6 months, documented by persistent elevated cardiac enzymes or persistent regional wall abnormalities on assessment of LVEF function
  - History of documented congestive heart failure (New York Heart Association functional classification III-IV)

- Documented cardiomyopathy
12. Patient has poorly controlled diabetes mellitus or steroid-induced diabetes mellitus
  13. Other concurrent severe and/or uncontrolled concomitant medical conditions (e.g., active or uncontrolled infection) that could cause unacceptable safety risks or compromise compliance with the protocol
    - Significant symptomatic deterioration of lung function. If clinically indicated, pulmonary function tests including measures of predicted lung volumes, DLco, O2 saturation at rest on room air should be considered to exclude pneumonitis or pulmonary infiltrates.
  14. Impairment of gastrointestinal (GI) function or GI disease that may significantly alter the absorption of BKM120 (e.g., ulcerative diseases, uncontrolled nausea, vomiting, diarrhea, malabsorption syndrome, or small bowel resection). Patients with unresolved diarrhea will be excluded as previously indicated
  15. Patients who are currently receiving treatment with medication with a known risk to prolong the QT interval or inducing Torsades de Pointes and the treatment cannot either be discontinued or switched to a different medication prior to starting study drug. Please refer to Table 18 for a list of prohibited QT prolonging drugs with risk of Torsades de Pointes.
  16. Patients receiving chronic treatment with steroids or another immunosuppressive agent.
    - **Note:** Topical applications (e.g. rash), inhaled sprays (e.g. obstructive airways diseases), eye drops or local injections (e.g. intra-articular) are allowed. Patients with previously treated brain metastases, who are on stable low dose corticosteroids treatment (e.g dexamethasone 2 mg/day, prednisolone 10 mg/day) for at least 14 days before start of study treatment are eligible.
  17. Patients who have taken herbal medications and certain fruits within 7 days prior to starting study drug. Herbal medications include, but are not limited to St. John's wort, Kava, ephedra (ma huang), ginkgo biloba, dehydroepiandrosterone (DHEA), yohimbe, saw palmetto, and ginseng. Fruits include the CYP3A inhibitors Seville oranges, grapefruit, pummelos, or exotic citrus fruits.

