
a ≥ CTCAE grade 3 anemia will not be considered DLT unless judged to be a hemolytic process secondary to study drug. ≥ CTCAE grade 3 lymphopenia will not be considered DLT unless clinically significant.
 
b For any grade 3 or 4 hepatic toxicity that does not resolve within 7 days to ≤ grade 1 (or ≤ grade 2 if liver infiltration with tumor present), an abdominal CT scan has to be performed to assess if it is related to disease progression.
 
A single patient is assumed not to tolerate the dose if he/she experiences at least one DLT. If a lower grade AE leads to a dose interruption of more than 7 doses of BKM120, this AE will be considered as DLT.
 
If the 2nd occurrence of an initially non-dose limiting toxicity (e.g., grade 3 AST that resolved to ≤ grade 1 within 7 days at 1st occurrence) leads to a dose reduction ( Section 6) within 28 days of the first dose of BKM120, this will be considered a DLT.
	

The investigator must notify the sponsor immediately of any unexpected ≥ CTCAE grade 3 adverse events or laboratory abnormalities. Prior to enrolling patients into a higher dose level, ≥ CTCAE grade 2 adverse events will be reviewed for all patients at the current dose level.

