## APPENDIX B: DRUGS THAT ARE PROHIBITED

- Other investigational therapies must not be used while the patient is on the study.
- Anticancer therapy (chemotherapy, biologic or radiation therapy, and surgery) other than the study treatments must not be given to patients while the patient is on the study. If such agents are required for a patient then the patient must be discontinued from the study.
- In *vitro* metabolism studies suggest that oxidative metabolism of BKM120 is predominantly mediated by CYP3A4 (fm>0.9), with only minor contributions of CYP1A1. As BKM120 is a sensitive CYP3A4 substrate, co-administration of BKM120 with strong and moderate CYP3A4 inhibitors and CYP3A4 inducers is prohibited. See below for a list of prohibited drugs. Please note this list may not be comprehensive.
- Based on in vitro studies, co-administration of BKM120 with CYP3A4 inducers is predicted to decrease the systemic exposure to BKM120, thereby increasing the risk of exposing the patient to subtherapeutic drug levels. See below for a list of prohibited CYP3A inducers. Please note that this list may not be comprehensive. Therapeutic doses of warfarin sodium (Coumadin®) or any other coumadin-derivative anticoagulants are not permitted.
- If a patient requires the concomitant use of any medication included in Table 18 below entitled “List of Prohibited QT prolonging drugs” (i.e., drugs that are generally accepted by the Qtdrugs.org Advisory Board of the Arizona CERT to have a risk of causing Torsades des de Pointes), study treatment administration must be interrupted as long as the patient requires therapy with the QT prolonging agent.
- Herbal preparations/medications are not allowed throughout the study. These herbal medications include, but are not limited to St. John’s wort, Kava, ephedra (ma huang), ginko biloba, dehydroepiandrosterone (DHEA), yohimbe, saw palmetto, ginseng. Patients should stop using these herbal medications 7 days prior to first dose of study drug.
- Hormonal contraceptives may be affected by cytochrome P450 interactions, and are therefore not considered effective in this study.

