**Table 20: LIST OF QT PROLONGING DRUGS TO BE USED WITH CAUTION**

Drug	QT risk	Comment
Alfuzosin	possible risk for Torsades de Pointes	
Amantadine	possible risk for Torsades de Pointes	
Amitriptyline	conditional risk for Torsades de Pointes	
Azithromycin	possible risk for Torsades de Pointes	
Chloral hydrate	possible risk for Torsades de Pointes	
Citalopram	conditional risk for Torsades de Pointes	
Clomipramine	conditional risk for Torsades de Pointes	
Clozapine	possible risk for Torsades de Pointes	
Desipramine	conditional risk for Torsades de Pointes	
Diphenhydramine	conditional risk for Torsades de Pointes	

Drug	QT risk	Comment
Dolasetron	possible risk for Torsades de Pointes	
Doxepin	conditional risk for Torsades de Pointes	
Dronedaron	possible risk for Torsades de Pointes	
Felbamate	possible risk for Torsades de Pointes	
Flecainide	possible risk for Torsades de Pointes	
Fluoxetine	conditional risk for Torsades de Pointes	
Foscarnet	possible risk for Torsades de Pointes	
Fosphenytoin	possible risk for Torsades de Pointes	
Galantamine	conditional risk for Torsades de Pointes	
Gatifloxacin	possible risk for Torsades de Pointes	
Gemifloxacin	possible risk for Torsades de Pointes	
Granisetron	possible risk for Torsades de Pointes	
Imipramine	conditional risk for Torsades de Pointes	
Indapamide	possible risk for Torsades de Pointes	
Isradipine	possible risk for Torsades de Pointes	
Levofloxacin	possible risk for Torsades de Pointes	
Lithium	possible risk for Torsades de Pointes	
Mexiletine	conditional risk for Torsades de Pointes	
Moexipril/HCTZ	possible risk for Torsades de Pointes	
Moxifloxacin	possible risk for Torsades de Pointes	
Nicardipine	possible risk for Torsades de Pointes	
Nortriptyline	conditional risk for Torsades de Pointes	
Octreotide	possible risk for Torsades de Pointes	
Ofloxacin	possible risk for Torsades de Pointes	
Ondansetron	possible risk for Torsades de Pointes	
Oxytocin	possible risk for Torsades de Pointes	
Paliperidone	possible risk for Torsades de Pointes	
Paroxetine	conditional risk for Torsades de Pointes	
Perflutren lipid microspheres	possible risk for Torsades de Pointes	
Protriptyline	conditional risk for Torsades de Pointes	
Ranolazine	possible risk for Torsades de Pointes	
Risperidone	possible risk for Torsades de Pointes	
Roxithromycin*	possible risk for Torsades de Pointes	*not available in the United States
Sertindole	possible risk for Torsades de Pointes	

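### Appendix B's caution rule for QT-prolonging drugs cites the prohibited list (Table 18), not the caution list (Table 20), and three Table 18 drugs are both prohibited and permitted

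*Combined protocol and SAP*

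**What the plan says.** All of the following is in the combined protocol and SAP.

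- **Appendix B, drugs that are prohibited.** "If a patient requires the concomitant use of any medication included in Table 18 below", then "study treatment administration must be interrupted as long as the patient requires therapy with the QT prolonging agent".
- **Appendix B, Table 18, introduction.** "All QT-prolonging drugs listed in this table are prohibited for all patients from screening through permanent discontinuation of study treatment". It adds that the table mixes two groups: agents whose torsades risk is established, and agents of a lesser risk class that were added because they are sensitive CYP3A substrates.
- **Appendix B, drugs to be used with caution.** After enrolment, if a patient needs "any QT prolonging medication with a possible or conditional risk for torsade de pointes then the investigators, at their discretion, may co-administer such medications". Patients on such drugs have to be monitored. Then: "Refer to Table 18 for a list of QT prolonging medications to be used with caution". The note directly below calls Table 18 the prohibited list.
- **Appendix B, Table 20.** Its title is "LIST OF QT PROLONGING DRUGS TO BE USED WITH CAUTION".
- **Section 3.3, exclusion criterion 15.** A patient on a drug with known QT or torsades risk is excluded when "the treatment cannot either be discontinued or switched to a different medication prior to starting study drug". It cites Table 18 as the prohibited list.
- **Section 5.5, Table 9 footnote.** "If a lower grade AE leads to a dose interruption of more than 7 doses of BKM120, this AE will be considered as DLT". Section 5.5 itself restricts DLTs to events judged unrelated to concomitant medication, among other causes.

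**The concern.** The caution rule combines a permission with a monitoring duty, and both depend on the prescriber knowing which drugs are meant. The rule names the wrong table, and nothing else in the available text names the right one.

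The drugs left without a reference are not remote from this trial. Section 7.1.1.1 names sertraline and fluoxetine as treatment for mood alteration, and both are in Table 20. Section 5.8.2 gives a 5HT antagonist with cisplatin, and ondansetron, granisetron and dolasetron are in Table 20. Section 5.12.5 and the Section 10 calendar schedule an ECG at screening and afterwards only as clinically indicated, so QT vigilance on treatment leans on instructions like this one.

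The second issue is that Appendix B gives three instructions (prohibit, interrupt, co-administer at discretion) without saying how they rank when more than one reaches the same drug.

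**Working it through.** No figure in the plan is tied to this rule, so the check is mainly a side-by-side reading with counts.

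**1. How each table is cited.** Table 18 is used in five places: exclusion criterion 15, the interruption bullet, its own title and introduction, the caution rule, and the note beneath the caution rule. Four of the five treat it as the prohibited list. Only the caution rule treats it as a caution list. Table 20 appears only in its own title.

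**2. What the tables contain.**
- Table 18: 29 drugs = 26 known risk + 3 possible risk (quetiapine, tacrolimus, vardenafil).
- Table 20: 52 drugs, all possible or conditional risk.
- Drugs in both: 0.

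A prescriber who follows the reference therefore finds none of the 52 caution drugs. The only entries of a matching risk class are three drugs whose own rows say they are prohibited.

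**3. Which instruction reaches which drug.**

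| Group | Table 18 introduction | Interruption bullet | Caution rule, by its class wording |
|---|---|---|---|
| 26 known-risk drugs (Table 18) | Prohibited until permanent discontinuation | Interrupt study treatment while needed | Not covered |
| 3 possible-risk drugs (Table 18) | Prohibited until permanent discontinuation | Interrupt study treatment while needed | Discretionary, with monitoring |
| 52 drugs (Table 20) | Not listed | Not covered | Discretionary, with monitoring, but the list is not cited |

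Correcting the table number repairs the third row only. The second row still holds a ban and a permission for the same three drugs. In the first row the tension is between a ban with no end before permanent discontinuation and an interruption that implies treatment may resume.

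**4. Whether the primary endpoint is touched.** The Section 13 escalation probability is P = (1−p)³ + 3p(1−p)²(1−p)³. At p = 0.20 this is 0.512 + 0.384 × 0.512 = 0.709 (plan: .71). At p = 0.30 it is 0.343 + 0.441 × 0.343 = 0.494 (plan: .49). The maximum of 6 × 6 + 10 = 46 patients also reproduces. None of these uses the QT rules, so none changes.

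A route to the DLT count can be described. Suppose a lower-grade event is treated with one of the three drugs for more than seven days. The interruption bullet would then produce more than seven missed doses, and the caution rule would produce none. Whether those missed doses fall under the seven-dose clause is not stated. The documents give no rate of use of these drugs. Purely as an assumption, if such cases added 2, 5 or 10 percentage points to a counted DLT rate of 30%, P would fall from 0.494 to 0.454, 0.396 or 0.309. These values show sensitivity, not an expected effect.

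**The case against.** The best case for the plan is that this is a visible numbering slip. The note under the caution rule says Table 18 is prohibited, and anyone who turns to Table 18 reads the same at its head. Table 20 carries the right title, and sertraline and fluoxetine also appear in Table 19, which is correctly cited. The Table 18 introduction explains why lesser-risk drugs were added, and the rows for the three drugs repeat that they are prohibited. The interruption bullet sits under the prohibited-drugs heading and can be read as what to do when the ban cannot be kept.

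Much of this stands, and it limits the point. It does not remove it. Seeing that the reference is wrong does not tell the prescriber which table was meant. Table 19 flags sertraline and fluoxetine for metabolism, not for QT risk, and does not list the 5HT antagonists. The caution rule still has no wording that says how it relates to the three Table 18 drugs in its class.

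Four stronger readings are tempting and are not supported:

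- *Any prohibited drug may be given with BKM120.* The permission is limited to possible or conditional risk, so it does not reach the 26 known-risk drugs. The wrong reference does not widen it.
- *The DLT result depends on which line is read.* The seven-dose clause needs an adverse event that leads to the interruption. An interruption made only to allow another drug is not clearly that, and Section 5.5 removes events attributed to concomitant medication. That one patient can separate 1/6 from 2/6 is true of any reclassification in a 3+3 design.
- *The interruption bullet also stops cisplatin and radiation.* Table 11 (bilirubin rows) and Table 15 use study treatment in the setting of BKM120 dose adjustment, and the Section 5.1 rule on continuing the other components concerns holds for toxicity. The term could be clearer, but no contradiction is shown.
- *Criterion 15 contradicts Table 18.* The criterion is an eligibility test. The mismatch is confined to the period between screening and the first dose.

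**Conclusion.** The point holds in a limited form. The caution rule cites the wrong table, and the list it needs (52 drugs) is cited nowhere in the available text. Separately, 3 of 29 Table 18 drugs are prohibited by the table and permitted by the class wording of the caution rule. For the other 26 the ban and the temporary interruption are unreconciled in wording but may be a rule and its contingency.

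This rests on the tables as printed and on the absence of any other citation of Table 20 in the text available for review. A consequence for DLT counting is possible, unquantified and not demonstrated. The matter should be corrected because it sits in an operative safety instruction, but it is a drafting inconsistency and not a flaw in the dose-escalation design.

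**What to change.** Correct the table reference in the caution section of Appendix B so that the caution rule and the caution list match. Reconcile the interruption bullet, the Table 18 introduction and the caution rule into one consistent instruction for Table 18 drugs, and state explicitly how it applies to quetiapine, tacrolimus and vardenafil. Align the start of the prohibition between exclusion criterion 15 and Table 18. While the text is open, it would help to say what study treatment covers in the interruption bullet, and whether an interruption made only to allow a QT-prolonging drug enters the seven-dose DLT clause.

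Which clinical rule applies is for the sponsor to decide. The cost is an amendment to wording, with no added patients, visits or tests and no change to Section 13.

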**Table 19: LIST OF CYP450 SUBSTRATES TO BE USED WITH CAUTION**

CYP2C8	CYP2C9	CYP2C19	CYP3A**	
amodiaquine	celecoxib	amitriptyline	Adinazolam	felodipine1
cerivastatin	diclofenac	citalopram	alfentanil1,2	fentanyl2
pioglitazone	flurbiprofen	clobazam	alpha-dihydroergocryptine1	flunitrazepam
repaglinide	fluvastatin	clomipramine	Alprazolam	fluticasone1
rosiglitazone	glibenclamide (glyburide)	clopidogrel	Amlodipine	lovastatin1
torasemide	gliclazide	diazepam	Aripiprazole	maraviroc1
troglitazone	glimepiride	fluoxetine	Atorvastatin	midazolam1
	glipizide	imipramine	Brecanavir	nifedipine
	indomethacin	lansoprazole	brotizolam1	nisoldipine
	irbesartan	mephobarbital	budesonide1	nitrendipine
	ketobemidone	moclobemide	bupirone1	perospirone1
	lornoxicam	omeprazole	Capravirine	quinine
	losartan	pantoprazole	Cerivastatin	sildenafil1

	meloxicam	progesterone	Chlorpheniramine	simvastatin1
	naproxen	quazepam	cyclosporine2	sirolimus1,2
	nateglinide	rabeprazole	darifenacin1	tolvaptan
	piroxicam	sertraline	Diazepam	trazodone
	rosiglitazone	S-mephenytoin	diergotamine2	triazolam1
	S-ibuprofen		ebastine1	
	sulfamethoxazole		eletriptan1	
	tenoxicam		eplerenone1	
	tolbutamide		ergotamine2	
	torasemide		Estazolam	
	valdecoxib		everolimus1	

\* This database of CYP substrates was compiled from the Indiana University School of Medicine’s “Clinically Relevant” Table, and from (Zhou et al 2009)

\*\* CYP3A substrates were compiled from the Indiana University School of Medicine’s “Clinically Relevant” Table; and supplemented by the FDA’s “Guidance for Industry, Drug Interaction Studies” and the University of Washington’s Drug Interaction Database.

1 Sensitive substrates: Drugs whose plasma AUC values have been shown to increase 5-fold or higher when co-administered with a potent inhibitor of the respective enzyme.

2 Substrates with narrow therapeutic index (NTI): Drugs whose exposure-response indicates that increases in their exposure levels by the concomitant use of potent inhibitors may lead to serious safety concerns (e.g., Torsades de Pointes).

